9.1.4 Study Visits 2-12

The treatment period is defined as Randomization Study Visit 1 through Study Visit 12. During the study treatment period, any AE associated with the target ulcer and all SAE of any kind will be recorded in the appropriate eCRF. Device deficiencies (DevD) will be recorded in a separate eCRF. The evaluation of all AE is described in Section 12, *Adverse Events*. All weekly visits

must be performed according to the study visit schedule (Section 17), preferably on the same day each week, to conduct all assessments and to assure compliance with treatment. A plus or minus one day visit window will be used for all study visits.

VLU subjects found to have target ulcer closure should continue the compression dressing. Appropriate treatment for DFU subjects found to have target ulcer closure is left to the Investigator's discretion. Appropriate treatment for VLU and DFU subjects, whose target ulcer is ready for and will be surgically closed, is left to the Investigator's discretion. If the Investigator believes the target ulcer is ready for surgical closure, then this procedure should be completed within the same week of the scheduled study visit. The next scheduled visit for subjects with closed target ulcers or subjects that will be surgically closed will be designated as End of Treatment Assessment Visit 14 and should occur in 7 (± 1) days.

All study procedures should occur in the order outlined in the protocol. Study Visits occurring outside the protocol specified visit window should be completed and recorded as a protocol deviation.

1. Subjects will be queried regarding any changes in general health and the use of concomitant medications.
2. Any AE associated with the target ulcer and all SAE of any kind reported since the last assessment will be recorded in the appropriate eCRF. DevD will be recorded in a separate eCRF (see "Section 12, *Adverse Events*" for reporting and evaluating AE). Also, subjects will be queried as to any additional ulcer-related interventions requiring hospital admission, surgical intervention or specialist referral since the last assessment.
3. Assess level of pain from NPWT dressing wear, since the previous study visit, using the VAS.
4. Prior to examination of the ulcer, remove compression bandaging (**for VLU subjects**) and photograph the NPWT topical dressing using the ARANZ Silhouette wound imaging and measurement device.

CONFIDENTIAL DOCUMENT

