5. Photograph and determine ulcer area (cm²), perimeter (cm), greatest depth (mm) and volume (cm³) for target ulcers that remain open or, if the target ulcer is closed or remained closed, photograph using the ARANZ Silhouette wound imaging and measurement device.
6. **For subjects whose target ulcer remained open during the treatment period or re-opened after initialing closing during the treatment period:**
 - Conduct an ulcer assessment using the modified Bates-Jensen wound assessment tool and record percentage tissue type/condition of peri-wound skin assessment (Normal, Erythematous, Edematous, Eczematous, Excoriated, Macerated, Indurated).

7. All females of child-bearing potential (including those who have had a bilateral tubal ligation) will undergo an exit urine pregnancy test upon completion or discontinuation from the study and the results will be analyzed and documented by the site personnel.
8. Document what next treatment is planned by the PI post-study for each target ulcer, regardless if open or closed.
9. Subject to complete satisfaction questionnaire
10. The subject will be exited from the study.

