9.4 STUDY METHODS AND MEASUREMENTS

For purposes of derivation of endpoints and subsequent analysis, study treatment refers to either PICO or tNPWT. Four individual negative pressure wound therapy devices are available for use during the study; the data for the study endpoints collected for each of these individual devices will be pooled to constitute the tNPWT treatment arm.

Primary Endpoint

The primary endpoint for this study is the percentage change in target ulcer area over the 12-week treatment period. Target ulcer area is defined as surface area as measured by the ARANZ Silhouette Device (18.2) at each study visit by the Investigator. The percentage change in target ulcer area over the 12-week treatment period is then defined as:

CONFIDENTIAL DOCUMENT
This document contains confidential information, which is the property of Smith & Nephew, Inc. Do not copy, disclose, or circulate without written authorization from the appropriate Smith & Nephew personnel

$$\text{Percentage change in target ulcer area} = \left(\left(\frac{\text{Area}_{SV13} - \text{Area}_{SV1}}{\text{Area}_{SV1}} \right) \times 100 \right)$$

In cases where the target ulcer area is closed in the opinion of the Investigator (regardless of 1-week confirmation), the ulcer area will be imputed as 0 cm², resulting in a percentage change in target ulcer area of 100%. In circumstances where the ulcer area is missing at the Study Visit 13 for subjects that have not withdrawn prematurely due to closure, the last observation carried forward (LOCF) method will be used.

Key Secondary Endpoints

The key secondary endpoints are the percentage change in the target ulcer dimensions not assessed as part of the primary endpoint, namely depth and volume. As defined for the primary endpoint, ulcer depth and volume will be measured by the ARANZ Silhouette Device at each visit by the Investigator, and the percentage change in depth and volume over the 12-week treatment period will then be defined as per the formula above replacing the area measurements with the corresponding depth and volume respectively.

Secondary Endpoints

The secondary endpoints are as follows:

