2. STUDY DESIGN

2.1 DESCRIPTION OF TRIAL DESIGN

This is a multi-center, Phase 4, randomized, open-labelled, comparative-effectiveness study in subjects with at least one lower extremity wound (VLU or DFU). Subjects will be randomized to one of two treatment groups to receive either PICO single-use NPWT system or ActiV.A.C. ® System, for 12 weeks, or until target ulcer closure (by surgical intervention or secondary intention), whichever occurs first.

The study consists of four periods: a 1-week run-in period (including screening Run-In Visit 1, Run-In Visit 2), a 12-week randomized treatment period (including Study Visit 1 through Study Visit 12), a 1-week end-of-treatment assessment period (including Study Visits 13, 14). Study Visit 14 serves as the end of study visit.

Following a 1-week run-in period, approximately 160 subjects meeting entry criteria will be randomly assigned to one of the two treatment arms in a 1:1 allocation ratio to receive treatment with either PICO single-use NPWT system or ActiV.A.C. ® system for 12 weeks with dressing changes as deemed required in the opinion of the investigator or required in the instructions for use (IFU).

Eligible subjects will receive treatment for 12 weeks (Visits 1 through 12), or until their wound closes or progressing sufficiently to become ready for surgical closure in the opinion of the investigator. Subjects whose wounds have closed, as assessed by the Investigator, prior to the 12th week of treatment (or Visit 12) will stop treatment and return for one further visit (Visit 14) to verify if the target ulcer remains closed for one week following the initial observation of ulcer closure. An ulcer which remains closed at this one week verification assessment is defined as having achieved complete wound closure in this study.

For those subjects who are randomized and who discontinue from the study prior to Visit 13 due to any reasons other than target wound closure, Visit 14 will serve as the early termination (ET) visit.

The size of the target ulcer, pain associated with target ulcer will be assessed for each subject at Run-In Visit 1 (screening). This information, along with the status of

Document Number: 1004313
Document Version: 06

Document Part: 000
Document Status: Released

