2.3 EFFICACY/SAFETY MEASURES AND ENDPOINTS

2.3.1 PRIMARY ENDPOINT

The primary endpoint for this study is the percentage change in target ulcer area over the 12-week treatment period. Target ulcer area is defined as surface area as measured by the ARANZ Silhouette Device at each study visit by the Investigator.

The percentage change in target ulcer area over the 12-week treatment period is

Document Number: 1004313

Document Part: 000

Document Version: 06

Document Status: Released

then derived using the baseline area and the area recorded at Study Visit 13. In cases where the target ulcer area is closed in the opinion of the Investigator (regardless of 1-week confirmation), the ulcer area will be imputed as 0 cm². In circumstances where the ulcer area is missing at the Study Visit 13 for subjects that have not withdrawn prematurely due to closure, the last observation carried forward (LOCF) method will be used.

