2.3.5 HANDLING OF MISSING, INCOMPLETE, AND REPEAT DATA

The handling of missing data and/or missing planned visits is described in the following section for the primary endpoint and secondary endpoints.

Percentage change in ulcer Area – Primary Endpoint:

The percentage change in target ulcer area over the 12-week treatment period is derived using the baseline area and the area recorded at Study Visit 13. Missing values and/or visits may occur at these visits if data is not collected or a subject discontinues from the treatment due to wound closure or early termination. In cases where the target ulcer area is missing or an ARANZ image cannot be taken due to the ulcer being closed in the opinion of the Investigator, the ulcer area at the Study Visit will be imputed as 0 cm².

In circumstances where the ulcer area is missing at the Study Visit 13 for subjects that have not withdrawn prematurely due to closure, the last observation carried forward (LOCF) method will be used.

Percentage change in ulcer Depth/Volume – Key Secondary Endpoint:

The methods detailed above for the handling of missing/incomplete data regarding the primary endpoint will also be used for Depth and Volume.

Proportion of subjects with confirmed ulcer closure – Secondary Endpoint:

The subject's ulcer closure status (open or closed) will be assessed by the Investigator at each study visit. Closure is confirmed at one-week post initial ulcer closure. Missing values and/or visits may occur at these visits if data is not collected at the Study Visit, or a subject discontinues from the treatment due to wound closure or early termination. Missing data may also exist if the one-week closure

Document Number: 1004313
Document Version: 06

Document Part: 000
Document Status: Released

ST:

9 7 5

Reference:

CE/052/PIC

Customer Code:

0 5

confirmation visit is not attended. In cases where the ulcer closure status is missing at a Study Visit or the subject is withdrawn from the study, the Last Observation Carried Forward (LOCF) method will be used (with the exception of the confirmatory period).

In addition, two separate sensitivity derivations will be performed to account for missing data:

- Worst case: In cases where subjects had missing data over the confirmatory target ulcer closure period (1 week follow-up) and it is unknown whether the closure is confirmed, these will be imputed as: Confirmed Closure=No.

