15. The change in target ulcer area during the screening period will be derived as (change in depth and volume will be derived using the same method):

$$Area_{Run-In\ 2} - Area_{Run-In\ 1}$$

16. The percentage change in target ulcer area during the screening period will be derived as (percentage change in depth and volume will be derived using the same method):

$$\left(\frac{Area_{Run-In\ 2} - Area_{Run-In\ 1}}{Area_{Run-In\ 1}} \right) \times 100$$

17. Target ulcer area is defined as surface area as measured by the ARANZ Silhouette Device at each study visit by the Investigator. For each study visit, the change in target ulcer area will be derived as (change in depth and volume will be derived using the same method):

$$\text{Change in target ulcer area at Study Visit } n = Area_{SVn} - Area_{SV1}$$

18. For each study visit, the percentage change in target ulcer area will be derived as (percentage change in depth and volume will be derived using the same method):

$$\text{Percentage change in target ulcer area at Study Visit } n = \left(\frac{Area_{SVn} - Area_{SV1}}{Area_{SV1}} \right) \times 100$$

For purposes of the primary analysis, the percentage change in target ulcer area will be derived as using LOCF within the 12-week treatment period. The percentage change in depth and volume will be derived using the same method.

19. The time to achieve confirmed ulcer closure in days will be derived as follows:
- For those subjects that achieve confirmed closure (derived variable 20):
Date of Study Visit where closure is first recorded – Date of Randomization
 - For those subjects that achieve closure but do not achieve confirmation (derived variable 20):
Date of Study Visit where closure is first recorded – Date of Randomization
 - For those subjects that do not achieve closure during the 12-week treatment period or withdraw early, the time to achieve confirmed ulcer closure will be defined as either: Date of last study visit attended – Date of Randomization;
Or 84 days, whichever occurs earlier.

20. Whether confirmed ulcer closure was achieved will be derived as follows:

- Ulcer Closed/Ready for surgical closure=Yes at last attended Study Visit i, Ulcer Closed=Yes at Follow up assessment (Visit 14). Confirmed Closure = Yes
- Ulcer Closed/Ready for surgical closure =Yes at last attended Study Visit i, Ulcer Closed=No at Follow up assessment (Visit 14). Confirmed Closure = No

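### An ulcer called closed counts as a 100% reduction in the primary and key secondary endpoints even when Visit 14, within the 12 weeks, finds it re-opened

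*Protocol*

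**What the plan says.** **The endpoint rule.** Protocol 9.4 (Primary Endpoint) provides that when the target ulcer is "closed in the opinion of the Investigator (regardless of 1-week confirmation), the ulcer area will be imputed as 0 cm²", and adds that this counts as a 100% change. SAP 2.3.1 has the same rule. SAP 2.3.5 says that where no area is available because of "the ulcer being closed in the opinion of the Investigator, the ulcer area at the Study Visit will be imputed as 0 cm²", and applies the same method to depth and volume.

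**Carry-forward.** If the Visit 13 area is missing, "for subjects that have not withdrawn prematurely due to closure, the last observation carried forward (LOCF) method will be used" (Protocol 9.4). Subjects who left because of closure are outside that provision. SAP 4.3, derived variable 18, says that "the percentage change in target ulcer area will be derived as using LOCF within the 12-week treatment period". It does not say what happens to an area measured at Visit 14 after an earlier closure call.

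**Visit 14.** After a closure call the next visit "will be designated as End of Treatment Assessment Visit 14 and should occur in 7" (±1) days (Protocol 9.1.4). Protocol 9.1.6 has open ulcers measured there for area, depth and volume. It also provides for an ulcer that "re-opened after initialing closing during the treatment period". The subject then leaves the study.

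**The closure endpoints.** Here the one-week check decides: "An ulcer which remains closed at this one week verification assessment is defined as having achieved complete wound closure in this study" (SAP 2.1). An ulcer found open at Visit 14 is scored as not confirmed (Protocol 9.4; SAP 4.3, derived variable 20).

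**The concern.** Take a subject called closed at week 4 and measured open at week 5. The last observation is an open wound with a known area, but the primary analysis records complete healing at week 12. The zero rests on the judgement of an investigator who knows the treatment. For healing by secondary intention, no area is determined at the closure visit; the ulcer is photographed and marked as closed.

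The planned analyses of area, depth and volume do not test this. They vary the population, the covariates and the distributional assumptions, and none substitutes the Visit 14 value. The Per Protocol Population, which is primary, admits subjects who achieve closure whatever their time on therapy and does not ask for confirmation, so both populations can carry the same zero. The sensitivity analyses that use the one-week check belong to the closure proportion and time-to-closure endpoints.

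At stake are the size of the reduction reported in each arm and, if closure calls hold up less well in one arm, the non-inferiority conclusion.

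**Working it through.** **1. The plan's own figures.** Protocol 11 gives margin 12.5, SD 24.5, one-sided 0.025, 80% power, 128 evaluable and 160 randomized. A two-look calculation at half the information, with the stated bounds (efficacy Z 2.963, futility Z 0.559) and a final bound of 1.969, gives 80.2% power at 128. Allowing for dropout, 128 / 0.80 = 160. These figures reproduce and the present point does not change them.

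**2. Which closures have an in-window Visit 14?** Visits are weekly, so Visit k falls near day 7 × (k − 1).

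| Closure first recorded | Nominal day | Visit 14, nominal day | Within 84 days? |
|---|---|---|---|
| Visit 2 | 7 | 14 | yes |
| Visit 5 (week 4) | 28 | 35 | yes |
| Visit 12 | 77 | 84 | at the end |
| Visit 13 | 84 | 91 | no |

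The problem is therefore confined to closures first recorded before Visit 13.

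**3. Effect on one arm.** Reduction is counted as positive, as in the protocol's prose. Let c be the share called closed, r the share of those that re-open, and g the Visit 14 area as a percentage of baseline. The overstatement of the arm mean is c × r × g. The documents give none of the three, so these are assumptions: c = 30% in both arms, r = 10-25%, g = 30-50.

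- Share affected: 0.30 × 0.10 = 3% to 0.30 × 0.25 = 7.5%.
- Overstatement: 0.03 × 30 = 0.9 points to 0.075 × 50 = 3.75 points.

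**4. Effect on the contrast.** With the same c, r and g in both arms the overstatements cancel and the bias is zero. The largest excess within the assumed range is 7.5% − 3% = 4.5 percentage points. With g equal in both arms:

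- g = 30: 0.045 × 30 = 1.35 points (1.35 / 12.5 = 11% of the margin).
- g = 50: 0.045 × 50 = 2.25 points (2.25 / 12.5 = 18% of the margin).

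**5. Effect on the error rate.** With 64 per arm, SE = 24.5 × √(2/64) = 4.33. The 95.4% interval implies a one-sided level of 2.3%, critical value 1.995. At a true PICO deficit of exactly 12.5, with the excess in the PICO arm, the chance of concluding non-inferiority is Φ(−1.995 + bias/4.33):

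| Bias (points) | Chance |
|---|---|
| 0 | 2.3% |
| 1.35 | 4.6% |
| 2.25 | 7.0% |

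This is a single-look approximation without covariate adjustment.

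**The case against.** **The rule is deliberate.** It is stated alike in both documents, and the primary endpoint measures change over the treatment period while the closure endpoints measure durable closure. A reader might infer that the two contradict each other. They do not; they answer different questions. It also stands that the Visit 14 value is off treatment, and that for a closure first seen at Visit 13 it comes after the endpoint. Zero is defensible there.

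**Visit 14 is not an independent check.** A reader might infer that an unblinded call overrides an objective one. The same open-label site reads Visit 14. Closure also has a definition (full epithelial cover, no drainage, no dressing needed), and the closed ulcer is photographed, although no blinded reading is planned.

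**Bias towards PICO is not shown.** A reader might infer that the rule favours PICO. The documents give no reason to expect unequal re-opening. A reader might also posit a 10-point excess with 30% residual area, hence 3.0 points and about 9.6%. That would need 33% of PICO closures to re-open against none in the control arm, or 43% against 10%, which is outside the 10-25% range assumed here.

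**Imbalance would be visible.** SAP 4.10 summarizes Visit 14 status, including re-opened ulcers, and SAP 4.1 splits summaries by treatment. This holds, but a table of counts does not correct the primary estimate.

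**The text is not airtight.** Protocol 9.1.6 orders measurement of ulcers that are still open and names re-opened ulcers only in the next step. Measuring them is the natural reading. Similarly, derived variable 18 could be read as picking up an in-window Visit 14 area, but the explicit instruction to disregard confirmation points the other way.

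**Conclusion.** The point holds for closures first recorded before Visit 13. A stated rule replaces a later, in-window measurement of an open ulcer with a perfect score on area, depth and volume, and no planned analysis of those endpoints shows what difference this makes.

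Each arm's mean reduction is overstated whenever ulcers re-open, by 0.9-3.75 points under the assumptions above. The contrast is biased only if re-opening rates or residual areas differ between arms. With 30% called closed in each arm, re-opening between 10% and 25%, and a common residual area of 30-50%, the largest shift is 1.35-2.25 points and the false non-inferiority rate at the margin is about 4.6-7.0% instead of 2.3%. Unequal residual areas could widen or narrow this. The rates are illustrative, and the direction could equally run against PICO. This is a weakness in the endpoint definition, not a contradiction, and it does not affect the sample size.

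**What to change.** In Protocol 9.4, SAP 2.3.1 and SAP 2.3.5:

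- For a closure first recorded before Visit 13 whose Visit 14 assessment shows the ulcer open, use the area, depth and volume measured at Visit 14 as the final values.
- Keep 0 for confirmed closures and for closures first seen at Visit 13.
- State how the rule applies to surgically closed ulcers. These have area, depth and volume measured at the visit where surgical closure is decided.
- Align SAP 4.3, derived variable 18, with the rule.

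Add two sensitivity analyses in both the Per Protocol Population and the Full Analysis Set: the current rule, and one that treats a missing Visit 14 confirmation as not closed and carries forward the last measured open area.

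At minimum, leave the primary definition as it is and pre-specify the Visit 14 substitution as a sensitivity analysis of the primary endpoint in both populations.

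The cost is a wording change to both documents, with no new data collection and no change to 128 or 160. It does alter slightly what the primary endpoint measures. The mean reduction becomes a little less favourable, and the substituted value is an off-treatment measurement taken one week after closure.
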